7.1.2. CAB Injection, Compartmental PK Sampling, and Follow-up

Procedures	Day 1			Day 3	Day 5	Day 8	Week 4	Week 8	Week 12	Week 24	Week 36	Week 52	Withdrawal ¹
	Pre-dose ²	0h	4h	48h	96h	168h							
Interim Medical / Medication / Drug / Alcohol History	X												
Brief Physical Exam (Section 7.4.3)	X												X
Vital Signs (Section 7.4.4)	X			X	X	X	X	X	X	X	X	X	X
Pregnancy Test (Section 7.4.6)	X						X	X	X	X	X	X	X
Hematology with differential; Clinical Chemistry Tests (Section 7.4.6)	X						X	X	X				X
HIV Test (Section 7.4.6)									X	X	X	X	X
STD testing (Section 7.4.6)	X												
Administer CAB LA 600 mg IM		X											
Injection Site Reaction Assessment		X	X	X	X	X	X	X	X	X	X	X	X
AE Assessment ³	X	X	X	X	X	X	X	X	X	X	X	X	X
Concomitant Medication Review	X			X	X	X	X	X	X	X	X	X	X
Blood plasma PK Sampling	X		X	X	X	X	X	X	X	X	X	X	X
Luminal Fluid (CVF/RF) PK Sampling ⁴				X		X	X	X	X				
Tissue PK Sampling ⁴ (Table 4)				X ⁵		X	X	X ⁵	X				
MRI ⁶		X		X		X							

- Subjects who terminate before week 52 will be asked to return to the site for a withdrawal visit.
- On Day 1, study personnel must verify the following pre-dose assessments to be within normal limits prior to injection: brief physical exam, vital signs, pregnancy test (negative; FRP only), AE assessment, and concomitant medication assessment. If a clinical abnormality, clinically significant AE, or prohibited medication that precludes injection is observed/recorded, the medical monitor must be contacted for further instruction.
- AE assessment will include a brief, symptom-directed physical exam as needed.
- Female subjects may consent to have paired rectal tissue and rectal fluid samples collected at each time-point. Female subjects who do not wish to participate in rectal PK sampling may still participate in the study.
- Vaginal tissue will be collected only on Day 3 (48 hour) and Week 8.
- Non-contrast MR Imaging will be performed in a subset of up to 8 subjects (4 males and 4 females). The MRI at 0h will be performed immediately after CAB injection and before the 4h blood plasma PK assessment.

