4.1.2. Oral Lead-in Phase

Subjects that are eligible to participate will return to the clinic on Day 1 of the oral lead-in phase and receive their first oral dose of CAB 30 mg after the completion of all pre-dose assessments as outlined in the Time and Events Table (Section 7.1). Subjects will be dispensed a sufficient supply of oral CAB 30 mg tablets to complete 27 days of once daily dosing at home and be counseled to take their dose at about the same time each day. On Day 14 of the oral lead-in phase, subjects will return to the clinic to assess safety, tolerability, and subject adherence to study drug. Subjects should bring their supply of oral CAB to the Day 14 visit to have drug accountability performed.

Subjects will return to the clinic on Day 29 to have drug accountability, PK and all assessments performed as described in the Time and Events Table (Section 7.1). Subjects will undergo PK sampling of blood plasma and CT/VT/CVF (females) and/or RT/RF. Female subjects who consent to rectal tissue and rectal fluid sampling will have paired rectal and genital tract samples collected at each timepoint. Female subjects who do not wish to participate in rectal PK sampling may still participate in the study. Every attempt should be made to acquire PK samples approximately 24 hours after the last outpatient dose of CAB 30 mg. After receiving their last dose of oral CAB 30 mg on Day 28, subjects will begin a 14-42 day wash-out period, during which no CAB will be administered.

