16. Positive hepatitis C antibody test result at screening or within 3 months prior to first dose of study treatment
17. A positive pre-study drug/alcohol screen (specific drugs are listed in Section 7.4.6). A positive drug screen is permitted if due to a prescribed medication, provided that medication is not on the list of prohibited medications in Section 6.10.2 and approved by the investigator and medical monitor.
18. A positive test for HIV antibody.
19. A positive pre-study screen for sexually transmitted diseases including *Neisseria gonorrhoea* or *Chlamydia trachomatis*, Trichomonas, syphilis, or an active HSV genital lesion.
20. Presence of a tattoo or other dermatological condition overlying the buttocks which in the opinion of the investigator may interfere with the interpretation of injection site reactions.
21. The subject has participated in a clinical trial and has received an investigational product within the following time period prior to the first dosing day in the current study: 30 days, 5 half-lives or twice the duration of the biological effect of the investigational product (whichever is longer).
22. Exposure to more than four new chemical entities within 12 months prior to the first dosing day.

DIAGNOSTIC ASSESSMENTS AND OTHER CRITERIA

23. Where participation in the study would result in donation of blood or blood products in excess of 500 ml within a 56 day period.
24. Unwillingness or inability to follow the procedures outlined in the protocol.
25. Subject is mentally or legally incapacitated.

Additional Criteria for Female Subjects Only:

26. Any current medical conditions that in the opinion of the investigator may compromise the conduct or analysis of the genital tract sampling (e.g., active genital tract infection or lesions).
27. Inability to abstain from the use of intravaginal products (e.g. tampons, spermicides, lubricants, vaginal hygiene products, diaphragms) for 72 hours prior to the genital tract sample collection visits and for up to 72 hours after.
28. Inability to abstain from any sexual activity (e.g., vaginal intercourse, masturbation, and penetration of the vagina by penises, fingers, tampons, sex toys) for 72 hours prior to the genital tract sample collection visits and for up to 72 hours after.

Additional Criteria for Male Subjects and Female Subjects who consent to rectal PK sampling:

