5.4.1. Liver Chemistry Stopping Criteria

For subjects with ALT elevation $\geq 1.25x$ but $< 3xULN$, retest ALT within one week. If the retest ALT is $< 1.25x ULN$, subjects may continue to Day 28 dosing. If the retest ALT is $\geq 1.25x ULN$, dosing will be terminated, and subjects are prohibited from entering the injection phase. Weekly assessments should be conducted until ALT is $< 1.25x ULN$. For subjects with ALT elevation $\geq 1.25x ULN$ at Day 29, dosing will be terminated, subjects are prohibited from entering the injection phase, and weekly assessments should be conducted until ALT is $< 1.25x ULN$. Subjects with ALT $\geq 3xULN$ at any time point will be discontinued from study treatment. Please refer to the Liver Safety Required Actions and Follow up Assessments Section in [Appendix 2](#) for subsequent evaluations. If any of the above develops, please notify the medical monitor.

[figure not shown]
Standard liver chemistry stopping and increased monitoring criteria have been designed to assure subject safety and evaluate liver event etiology (in alignment with the

FDA premarketing clinical liver safety guidance).

<http://www.fda.gov/downloads/Drugs/GuidanceComplianceRegulatoryInformation/Guidances/UCM174090.pdf>

Study treatment will be discontinued **for a subject** if liver chemistry stopping criteria are met prior to CAB LA injection. If liver stopping criteria are met after receiving a CAB LA injection, subjects will not be withdrawn from the study but continue to have safety assessments performed as noted below and within the Time and Events table for 52 weeks post-injection or until resolution of the liver event, whichever is longer.

Liver Chemistry Stopping Criteria – Liver Stopping Event Algorithm

Liver Safety Required Actions and Follow up Assessments Section can be found in [Appendix 2](#).

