7.1. Time and Events Table

7.1.1. Screening and Oral Lead-in Phase

Study Period	Screening ¹	Oral Lead-in ⁷			Washout Period
		Dosing Days 1-28			
Visit Window	Within 30 days of oral lead-in	Day 1	Day 14	Day 29	14 – 42 days
Informed Consent	X				
Demographics	X				
Medical / Medication / Drug / Alcohol History	X				
Eligibility Assessment - Inclusion/Exclusion Criteria	X				
Height, Weight, BMI	X				
Physical Exam	X				
Vital Signs (Section 7.4.4) ²	X	X	X	X	
12-Lead ECG (Section 7.4.5)	X	X	X		
Drug / Alcohol Screen (Section 7.4.6) ²	X	X			
Pregnancy Test (Section 7.4.6) ²	X	X		X	
Hepatitis B, Hepatitis C Screening (Section 7.4.6)	X				
HIV Test (Section 7.4.6)	X			X	
STD Screening (Section 7.4.6)	X				
Urine Dipstick Screening (Section 7.4.6)	X				
Hematology with differential; Clinical Chemistry Tests (Section 7.4.6) ²	X	X	X	X	
Coagulation Tests (Section 7.4.6)	X			X	
Administer oral CAB ³		X	X		
Dispense Oral lead-in IP		X			
Dispense Medication Dosing Diary		X			
Drug accountability/ pill count/review drug diary			X	X	
Blood plasma PK sampling				X	
Tissue/CVF/RF PK sampling ⁴				X	
AE Assessment ⁵		X	X	X	
Concomitant Medication Review		X	X	X	
PGx ⁶		← X →			

1. Screening may occur over more than one visit but within 30 days of the first dose of oral CAB 30 mg in the oral lead in phase.
2. Prior to administering the first oral dose of CAB, study personnel must verify the following pre-dose assessments to be within normal limits prior to administration: vital signs, pregnancy test (negative; FRP only). The results of the Drug/Alcohol screen, hematology with differential, and clinical chemistry tests on Day 1 are not required prior to administering the first oral dose of CAB 30 mg, but should be drawn prior to CAB administration.
3. Oral CAB dosing for Days 1 to 28. Day 29 assessments to be performed within 24 hours from the last dose on Day 28.
4. Female subjects may consent to have paired rectal tissue and rectal fluid samples collected at each time-point. Female subjects who do not wish to participate in rectal PK sampling may still participate in the study.
5. AE assessment will include a brief, symptom-directed physical exam as needed.
6. PGx: Can be collected any time; however, it is preferable to collect the sample at the earliest convenient time after the first dose in the oral lead in phase.

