7.3. Screening

All clinical and laboratory assessments of eligibility must be performed and reviewed within 30 days of initiating the oral lead-in phase. All Screening results must be available prior to enrollment.

Eligibility criteria must be carefully assessed at the Screening visit and confirmed at the Day 1 Oral lead-in phase visit and re-confirmed prior to injection.

Subjects may be enrolled and begin the oral lead-in phase as soon as all Screening assessments are complete and the results are available and documented.

Subjects who meet all entry criteria are enrolled and assigned a subject number. Subjects not meeting all inclusion and exclusion criteria at initial screen may be re-screened one time with a new subject number. Subjects who are enrolled into the trial and subsequently withdrawn from the study for any reason may not be rescreened.

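### The last scheduled HIV result is 13 to 41 days old when the single, irreversible CAB LA injection is given; a pre-dose HIV test could be added cheaply

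*Protocol*

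**What the plan says.** **Lead-in (Protocol 7.1.1).** HIV testing is marked at Screening and Day 29 only. Footnote 3 fixes the second of these: "Day 29 assessments to be performed within 24 hours from the last dose on Day 28".

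**Washout (Protocol 4.1.2).** "After receiving their last dose of oral CAB 30 mg on Day 28, subjects will begin a 14-42 day wash-out period".

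**Injection phase (Protocol 7.1.2).** The row beginning "HIV Test (Section 7.4.6" is blank from Day 1 pre-dose through Week 8. Its marks are at Weeks 12, 24, 36 and 52 and at Withdrawal. Pregnancy, chemistry, hematology and STD tests are all marked at Day 1 pre-dose. Table 5 defines the STD screen as gonorrhoea, chlamydia, syphilis and trichomonas, and lists HIV separately.

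**Check before dosing (Protocol 7.1.2, footnote 2).** On Day 1 "study personnel must verify the following pre-dose assessments to be within normal limits prior to injection". Five items follow: physical examination, vital signs, pregnancy test, adverse events and concomitant medication. An HIV result is not among them.

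**Eligibility (Protocol 7.3 and 5.2).** Eligibility is to be "confirmed at the Day 1 Oral lead-in phase visit and re-confirmed prior to injection". Exclusion 18 is "A positive test for HIV antibody". Section 7.3 does not say which sample serves for the re-confirmation.

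**The concern.** The injection is the one step in this study that cannot be undone. Section 4.6.1 expects residual drug for up to 52 weeks in some subjects and lists resistance after HIV acquisition as a risk. Section 5.4 names HIV acquisition among the reasons a subject may not be injected. Section 7.4.1.6 calls for immediate antiretroviral therapy if seroconversion follows the injection, because of possible resistance on monotherapy.

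The plan repeats several other tests on the day of injection but not this one. A symptom-free, unreported infection acquired between Day 29 and the injection would not stop the dose, and would next be looked for 84 days afterwards.

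**Working it through.** **Check of the calendar against the plan's own figure.** Protocol 4.2 gives participation of up to about 66 weeks. Screening 30 days + lead-in 28 + longest washout 42 + follow-up 52 × 7 = 364 gives 464 days, and 464 / 7 = 66.3 weeks. The stated figure is reproduced.

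**Age of the last scheduled HIV result at injection.**
- Injection day, on the lead-in calendar = 28 + washout = 28 + 14 to 28 + 42 = Day 42 to Day 70.
- Age of the Day 29 result = 42 − 29 to 70 − 29 = **13 to 41 days**.
- If the washout is counted from the Day 29 visit instead, the range is 14 to 42 days. The point is the same.

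**Interval between consecutive scheduled HIV tests.** Week 12 is 84 days after injection, so the interval is 13 + 84 = 97 to 41 + 84 = 125 days. A pre-dose test removes only the first part: 13 / 97 = 13% to 41 / 125 = 33% of the interval.

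**Expected infections acquired in the gap.** There are 16 injected subjects (Protocol 9.2.1). The assumed incidence is 0.1 to 1 per 100 person-years; the documents give none.

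| Wait, all subjects | Person-years = 16 × days / 365.25 | At 0.001 per year | At 0.01 per year |
|---|---|---|---|
| 13 days | 0.57 | 0.0006 | 0.0057 |
| 41 days | 1.80 | 0.0018 | 0.0180 |

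**How many of these the added test would find.** An antibody/antigen test needs time to turn positive. Take 14 to 28 days as an assumption (not in the documents).
- After a 13-day wait, none of the infections acquired in the gap would show.
- After a 41-day wait, only those from the first 41 − 28 = 13 to 41 − 14 = 27 days would show.
- At 0.01 per year this is 16 × 13 / 365.25 × 0.01 = 0.006 to 16 × 27 / 365.25 × 0.01 = 0.012.
- The test would also find an infection acquired shortly before Day 29 that was too recent to show then. With a constant detection delay and constant incidence, both kinds together span as many days as the gap, so 0.018 remains the ceiling.

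**The case against.** The strongest reply is that the sponsor saw this risk and dealt with it. Exclusion 12 bars recent high-risk behavior and exclusion 19 a positive STD screen. Section 7.4.1.6 requires possible exposures to be reported and adds HIV RNA testing if symptoms of acute infection appear. Injection Day 1 includes an interim history, an examination and STD testing. No rule in the documents sets a maximum age for the HIV result, and the expected count is tiny. All of this stands. What remains uncovered is an unreported, symptom-free infection in a low-risk volunteer.

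It is also fair that an antibody/antigen test may miss an infection acquired shortly before injection, and that the 84 days after injection are unaffected. Both limit the gain.

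A reader might go further and infer that the liver check before injection is missing too, since footnote 2 does not list chemistry. The documents do not support that:
- Chemistry is drawn at Day 1 pre-dose.
- Section 5.4.1 bars injection for a Day 29 ALT of 1.25 × ULN or more, and stops treatment "if liver chemistry stopping criteria are met prior to CAB LA injection".
- Re-confirmation under 7.3 takes in exclusion 1 (ALT or AST above ULN).
- The statement that "clinical chemistry tests on Day 1 are not required prior to administering the first oral dose of CAB 30 mg" applies to the oral Day 1 visit; the injection footnote contains no such waiver.

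At most, footnote 2 could be worded more clearly on this.

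**Conclusion.** The point holds as a cheap improvement for patient safety, of low severity (could be changed). The last scheduled HIV result is 13 to 41 days old at an irreversible dose, and the re-confirmation required by 7.3 has no HIV sample attached to it.

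The timing follows from the documents alone. The size, at most about 0.02 infections among 16 subjects, rests on the assumed incidence and on every subject waiting the full 41 days. The number of gap infections the test would actually detect is lower still. The case therefore rests on irreversibility and low cost, not on frequency.

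Two stronger readings should be avoided. The plan does not break a rule of its own, because 7.3 does not demand a fresh sample. Nor would the change close the whole 97 to 125 days between scheduled tests. No PK result is affected.

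**What to change.** In the Protocol 7.1.2 table, mark the HIV 1-2 Ab/Ag test already specified in Table 5 at Day 1 pre-dose, allowing it up to 3 days earlier. Add a negative HIV result to the footnote 2 list of items to verify before injection.

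The result would then be 0 to 3 days old at dosing. The cost is about 16 extra tests, one per injected subject. Blood is already drawn at Day 1 pre-dose, so no added invasive procedure is needed if the result can be had the same day. The documents do not state the laboratory turnaround; if it is slower, an earlier draw and possibly an extra visit would be needed. PK sampling is unchanged.

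No liver change is proposed. If the sponsor chooses to mention chemistry in footnote 2, any threshold must agree with both exclusion 1 and 5.4.1. A cut-off of 1.25 × ULN alone would pass a subject at 1.1 × ULN who fails exclusion 1 at the same step.

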7.2. Screening and Critical Baseline Assessments

Cardiovascular medical history/risk factors (as detailed in the CRF) will be assessed at screening.

Written informed consent must be obtained from each potentially eligible subject (or his or her legal representative) by study site personnel **prior** to the initiation of any screening procedures as outlined in this protocol. The consent form must have been approved by the Institutional Review Board/Institutional Ethics Committee (IRB/IEC). After signing an informed consent, subjects will complete screening assessments to determine subject eligibility. Each subject being screened for study enrolment evaluation will be assigned a subject number. This number will be given sequentially in chronological order of subject presentation.

Subjects must be counseled on the practice of safer sexual practices including the use of effective barrier methods (e.g. male condom) for the length of time in which they are required for participation in this study as part of the eligibility process.

The following demographic parameters will be captured: year of birth, sex, race and ethnicity.

Medical/medication/family history will be assessed as related to the inclusion/exclusion criteria listed in Section 5.

7.3. Screening

All clinical and laboratory assessments of eligibility must be performed and reviewed within 30 days of initiating the oral lead-in phase. All Screening results must be available prior to enrollment.

Eligibility criteria must be carefully assessed at the Screening visit and confirmed at the Day 1 Oral lead-in phase visit and re-confirmed prior to injection.

Subjects may be enrolled and begin the oral lead-in phase as soon as all Screening assessments are complete and the results are available and documented.

Subjects who meet all entry criteria are enrolled and assigned a subject number. Subjects not meeting all inclusion and exclusion criteria at initial screen may be re-screened one time with a new subject number. Subjects who are enrolled into the trial and subsequently withdrawn from the study for any reason may not be rescreened.

7.3.1. Baseline

Subjects will have “Baseline” assessments completed at Day 1 of the oral lead-in dosing period.

7.4. Safety

Planned time points for all safety assessments are listed in the Time and Events Table (Section 7.1). Additional time points for safety tests such as vital signs, physical exams and laboratory safety tests may be added during the course of the study based on newly available data to ensure appropriate safety monitoring.

In order to monitor safety and to respond to occurrences of toxicity expeditiously, the team will hold conference calls on a regular basis during study implementation, and additional conferences calls will take place on an *ad hoc* basis. Study site investigators will be responsible for close monitoring and management of AEs, and will have detailed SOPs for the reporting of AEs and the management of toxicity. The Safety Monitor will be responsible for providing support to study investigators regarding the clinical management of individual participants (including decision-making surrounding eligibility, discontinuation/holds/termination of study drug, and clinical management).

7.4.1. Adverse Events (AE) and Serious Adverse Events (SAEs)

The definitions of an AE or SAE can be found in [Appendix 3](#) and [Appendix 4](#). The DAIDS Table for Grading the Severity of Adult and Pediatric Adverse Events Version 2.0 (Section 12.4) will be employed to grade the severity of the detected adverse events.

For this study, the Sponsor considers seizures as an AE of special interest (see Investigator's Brochure for background information). Where seizures occur, the Sponsor would like to better characterize these occurrences to enable systematic analyses. Investigators are requested to document and report seizure or possible seizure events promptly (within 24 hours of learning of the event) to the Sponsor for evaluation and onward reporting. Data should be documented on the appropriate AE/SAE page (see Section 12.3).

The investigator and their designees are responsible for detecting, documenting and reporting events that meet the definition of an AE or SAE.

7.4.1.1. Injection Site Reactions

Injection Site Reaction (ISR) examination will include an assessment of pain, tenderness, pruritus, warmth, infections, rash, erythema, swelling, induration, and nodules (granulomas or cysts). Digital photographs will be documented on all subjects who have an ISR that are Grade 2 if persistent beyond 2 weeks, any Grade 3 or above, or are serious. Dermatology will be consulted on all subjects who have an injection site reaction considered serious, Grade 3 or above, or if persistent beyond 30 days and others if the Investigator or Medical Monitor feels it is medically necessary.

7.4.1.2. Time period and Frequency for collecting AE and SAE information

- AEs and SAEs will be collected from the start of Study Treatment until the follow-up contact (see Section 7.4.1.4), at the timepoints specified in the Time and Events Table (Section 7.1).

- Medical occurrences that begin prior to the start of study treatment but after obtaining informed consent may be recorded on the Medical History/Current Medical Conditions section of the CRF.
- Any SAEs assessed as related to study participation (e.g., protocol-mandated procedures, invasive tests, or change in existing therapy) or related to a GSK product will be recorded from the time a subject consents to participate in the study up to and including any follow-up contact.
- All SAEs will be recorded and reported to GSK within 24 hours, as indicated in [Appendix 3](#).
- Investigators are not obligated to actively seek AEs or SAEs in former study subjects. However, if the investigator learns of any SAE, including a death, at any time after a subject has been discharged from the study, and he/she considers the event reasonably related to the study treatment or study participation, the investigator must promptly notify GSK.

NOTE: The method of recording, evaluating and assessing causality of AEs and SAEs plus procedures for completing and transmitting SAE reports to GSK are provided in [Appendix 3](#). The relatedness of a given AE to the study product will be assessed by study investigators as described in [Appendix 3](#).

